4.1.4 Subject Enrollment and Randomization

Study participation begins (ie, a subject is "enrolled") once written informed consent is obtained. Once informed consent is obtained, a subject identification (SID) number will be assigned by an IXRS, and the screening evaluations may begin to assess study eligibility (inclusion/exclusion) criteria. The SID number will be used to identify the subject during the screening process and throughout study participation, if applicable.

A master log of all consented subjects will be maintained at the site and will document all screening failures (ie, subjects who are consented but do not meet study eligibility criteria and/or are not randomized), including the reason(s) for screening failure.

Subjects who fail to meet the inclusion/exclusion criteria (ie, screening failures) should not be randomized or receive investigational product.

4.1.5 Withdrawal from the Study

Subjects are free to withdraw from the study at any time (investigational product and assessments), without prejudice to further treatment (withdrawal of consent). Subjects who withdraw from the study will always be asked about the reason(s) for withdrawal, and about the presence of any adverse events (AEs). If possible, subjects who withdraw consent will be seen and assessed by the investigator. Adverse events will be followed up, and the ePRO device and the home peak flow meter should be returned by the subject. If a subject withdraws consent from further participation in the study, then no further study visits or data collection should take place.

4.1.6 Discontinuation of Investigational Product

An individual subject will not receive any further investigational product if any of the following occur in the subject in question:

- 1. Withdrawal of consent from further treatment with investigational product or lost to follow-up.
- 2. An AE that, in the opinion of the investigator or the sponsor, contraindicates further dosing.
- 3. Subject is determined (after randomization) to have met one or more of the exclusion criteria related to safety prior to being randomized in the study.
- 4. Pregnancy (see Section 5.6.3).

Subjects who prematurely discontinue receiving investigational product will be identified as having permanently discontinued treatment regardless of the reason (eg, withdrawal of consent, due to an AE, other).

When feasible, compliant subjects who are discontinued from receiving the investigational product should be encouraged to undergo all study related visits/procedures through Week 64 (Visit 32), including safety follow-up, in order to support the final efficacy and safety analyses for MEDI9929.

Subjects who are prematurely discontinued from receiving investigational product are encouraged to undergo all study-related visits/procedures through Week 64. If a subject is not willing to continue to participate in the study, the subject should return to the study site and complete procedures according to Visit 30 (Early Discontinuation Visit [EDV]) and return 12 weeks after the EDV for safety follow-up and protocol-specified assessments according to Visit 32 (Safety Follow-up Visit [SFV]). Study procedures including PRO assessments will continue until the SFV.

The EDV will be the final study visit, and the SFV will not be conducted, in the following circumstances.

- Consent is withdrawn specifically from further study participation (Section 4.1.5).
- The subject is lost to follow-up.
- The subject starts an alternative treatment (eg, one of the prohibited medications).
- The subject is enrolled in another clinical study.

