4.3 Description of Study Procedures

4.3.1 Efficacy

4.3.1.1 Assessment of Asthma Exacerbations

For the purpose of the protocol, an asthma exacerbation will be defined as a worsening of asthma that leads to any of the following:

- Use of systemic corticosteroids for at least 3 days.
 - A single depo-injectable dose of corticosteroids is considered equivalent to a 3-day course of systemic corticosteroids.
 - For subjects receiving maintenance OCS, a temporary doubling of the maintenance dose for at least 3 days qualifies.
- An ED visit due to asthma that required systemic corticosteroids (as per above).
- An inpatient hospitalization due to asthma.

Subjects may receive up to 7 days treatment with systemic corticosteroids for an asthma exacerbation and must return to their previous stable asthma treatment regimen at that time. Although a single depo-injection of intra-muscular corticosteroids is considered equivalent to a course of corticosteroids, this route of administration is discouraged and should not be administered by the investigator or designee.

Worsening of asthma is defined as new or increased symptoms and/or signs (examination or lung function) that can be either concerning to the subject (subject-driven) or related to an Asthma Daily Diary alert (diary-driven) via the ePRO device. The ePRO device will be programmed to alert both the subject and study center when certain pre-specified (objective) asthma-worsening thresholds are crossed including:

- Decrease in morning peak flow \geq 30% on at least 2 of 3 successive days compared with baseline (last 7 days of run-in), and/or
- $A \ge 50\%$ increase in rescue medication (minimum increase of 2 or more puffs, or one new or additional nebulized $\beta 2$ agonist) on at least 2 of 3 successive days compared with the average use for the previous week, and/or

- Nocturnal awakening due to asthma requiring rescue medication use for at least 2 of 3 successive nights, and/or
- An increase in total asthma symptom score (the sum of daytime [evening assessment] and nighttime [morning assessment]) of at least 2 units above the screening/run-in period average (last 10 days of screening/run-in), or the highest possible score (daily score of 6), on at least 2 of 3 successive days

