4.5.2 Additional Study Medications

All subjects will be taking medium- or high-dose ICS and LABA (see Appendix 5 for equivalent ICS doses) from Week -4 through Week 64. The cost of the ICS and LABA treatment will be reimbursed to the sites by the sponsor, where applicable.

If at Week -4 the subject is also taking additional asthma controller medications (including leukotriene modifiers, theophylline, cromones, or OCS up to a maximum of 10 mg daily or 20 mg every other day), then these medications should be continued at a stable dose during the screening/run-in period and to Week 64. Subjects who are taking theophylline should be monitored appropriately by the investigator during the conduct of this study.

The principal aim of this study is to establish the treatment effect of MEDI9929 as an 'add on' therapy; therefore, it is highly desirable that background asthma controller medications are maintained at a stable dose from Week -4 through Week 64, in order to prevent any independent confounding of that treatment effect. Symbicort should not be used as a rescue inhaler (eg, SMART regimen). However, if the investigator considers a permanent change to background medications between Week-4 (Visit 2) and Week 64 to be necessary, the change should be discussed with the sponsor's medical monitor and must be noted in the eCRF. The subject may remain in the study unless the addition of omalizumab is required, in which case the subject must be withdrawn.

During the study, subjects may use an inhaled short-acting bronchodilator or an inhaled short-acting anticholinergic on an as-required basis as a reliever or rescue medication.

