4.7.2 Prohibited Concomitant Medications

Other than the medications described above, use of concomitant medications including over-the-counter medications, herbal supplements, vitamins, etc, from screening (Week -5) through Week 64 is discouraged. Subjects must be instructed not to take any medications, including over-the-counter products, without first consulting with the investigator.

The following medications are considered exclusionary and are not permitted during the study. The sponsor must be notified if a subject receives any of these during the study

- Immunosuppressive medication (eg, methotrexate, troleandomycin, oral gold, cyclosporine, azathioprine, intramuscular long-acting depot corticosteroid).
- Oral corticosteroids for chronic use in diseases other than asthma; short bursts (≤ 7 days) of systemic corticosteroids for other acute inflammatory diseases are. permitted
- 5-lipoxygenase inhibitors (zileuton).
- Investigational agents other than MEDI9929.
- Marketed biologics including omalizumab.
- Immunoglobulin or blood products.
- Use of any oral or ophthalmic β -adrenergic antagonist (eg. propranolol).
- Live or attenuated vaccines.
- Subjects are not to begin allergen-specific immunotherapy from 2 months before Visit 1 (Week -5) through Week 64.
- Th2 cytokine inhibitor (suplatast).

See also Table 4.3.1.3-1 for prohibited medications prior to spirometry assessment.

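### Exacerbation follow-up can end because a subject starts a prohibited medicine or needs omalizumab, a reason tied to the outcome of the ITT primary analysis

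*Protocol*

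**What the plan says.** Protocol Section 4.1.6 (Discontinuation of Investigational Product) twice encourages subjects who stop product to continue all visits through Week 64, and gives support of the final efficacy and safety analyses as the reason. A subject unwilling to continue attends the early discontinuation visit (EDV) and returns 12 weeks later for the safety follow-up visit (SFV). The section then adds: "The EDV will be the final study visit, and the SFV will not be conducted, in the following circumstances". Beside withdrawn consent, loss to follow-up and entry into another trial, the list includes "The subject starts an alternative treatment (eg, one of the prohibited medications").

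Section 4.5.2 (Additional Study Medications), on permanent changes to background medication, says: "The subject may remain in the study unless the addition of omalizumab is required, in which case the subject must be withdrawn".

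Section 4.7.2 (Prohibited Concomitant Medications) bars marketed biologics, among others. Under immunosuppressants it also names "intramuscular long-acting depot corticosteroid". The only action it states is: "The sponsor must be notified if a subject receives any of these during the study". Section 4.3.1.1 (Assessment of Asthma Exacerbations) counts the depot route towards the primary endpoint: "A single depo-injectable dose of corticosteroids is considered equivalent to a 3-day course of systemic corticosteroids". It adds that "this route of administration is discouraged and should not be administered by the investigator or designee". The same section lets subjects who exacerbate stay on product if the investigator judges this appropriate.

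Sections 4.8.1 and 4.8.3.1 set an ITT primary analysis by randomized group. Nothing is imputed for the primary endpoint, and the model is negative binomial with follow-up time as an offset. The annual rate is presented as total events over total person-time. No section provides for collecting exacerbations after a Section 4.1.6 stop or an omalizumab withdrawal.

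**The concern.** A subject who starts another asthma treatment, or who needs omalizumab, is often one whose asthma is failing. Such a subject may be quite willing to answer a telephone call. Placing this case beside withdrawn consent and loss to follow-up treats a collectable outcome as uncollectable, and it works against the section's own reason for keeping subjects to Week 64.

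The offset treats the unseen time as if events would have continued at the rate the model assigns to that subject. If the rate changes after stopping, because drug effect is lost, the disease worsens or the new treatment works, the analysis does not estimate the effect over the full 52 weeks in all randomized and dosed subjects. No later analysis plan can recover data that were never collected.

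**Working it through.** **The plan's own figure.** Section 4.8.2 gives a placebo rate of 0.7, a 40% reduction (active rate 0.42), dispersion 0.7, two-sided alpha 0.1 and 80% power.

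n = (1.645 + 0.842)² × (1/0.7 + 1/0.42 + 2 × 0.7) / (ln 0.6)² = 123.4, so 124 per group. Then 124/0.9 = 137.8, so 138, and 4 × 138 = 552. All three figures reproduce and are not in question.

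**How the rules fit together.**
- The Section 4.1.6 list has two readings. On the broad one, any subject who starts an alternative treatment has the EDV as last visit. On the narrow one, only subjects already off product are meant, since prohibited medication is not among that section's four reasons to stop product.
- Section 4.5.2 withdraws subjects who need omalizumab from the study, so it applies on either reading.
- On both readings some subjects stop contributing data for a reason related to the outcome.

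The documents do not say how often this would happen. Both calculations below therefore rest on assumed inputs.

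**Calculation A: active-arm leavers revert to the placebo rate.** Let u be the share of active-arm time that is unobserved, and let placebo rates stay unchanged.

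Ratio = [0.42 × (1 − u) + 0.70 × u] / 0.70 = 0.60 + 0.40u

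- 5% leave at 6 months: u = 0.05 × 0.50 = 0.025, ratio 0.61.
- 15% leave at 3 months: u = 0.15 × 0.75 = 0.1125, ratio 0.645.

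The model fitted to observed time would report 0.60.

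**Calculation B: exacerbations end follow-up.** Simulation with gamma frailty (dispersion 0.7), 150,000 subjects per arm and a true ratio of 0.60. Each exacerbation ends follow-up with probability q, the same in both arms. The rate after stopping is 1, 1.5 or 2 times the rate before, in both arms.

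| q | Stopped early, placebo / active | Events per person-year, placebo / active | Fitted ratio (×1, ×1.5, ×2) | Full-follow-up ratio (×1, ×1.5, ×2) |
|---|---|---|---|---|
| 0.05 | 3.4% / 2.0% | 0.69 / 0.42 | 0.603, 0.600, 0.603 | 0.604, 0.598, 0.597 |
| 0.10 | 6.7% / 4.0% | 0.68 / 0.41 | 0.599, 0.598, 0.598 | 0.600, 0.591, 0.585 |
| 0.20 | 12.5% / 7.8% | 0.67 / 0.41 | 0.598, 0.601, 0.605 | 0.598, 0.590, 0.583 |
| 0.30 | 17.8% / 11.2% | 0.66 / 0.40 | 0.599, 0.598, 0.600 | 0.601, 0.582, 0.569 |

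The stopped and person-year columns are from the runs with an unchanged rate.

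- Stopping is unequal between arms because it follows the outcome.
- With an unchanged rate after stopping, the fitted ratio agrees with the full-follow-up ratio. The model copes with stopping that depends only on observed events.
- With a changed rate the two separate: about 0.60 fitted against 0.58 (q = 0.20) or 0.57 (q = 0.30) when the rate doubles.
- The presented rate falls even with an unchanged rate after stopping. At q = 0.20 it is 0.67 instead of 0.70 on placebo. The crude ratio is then 0.407/0.669 = 0.61.

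Calculation A puts the full-follow-up ratio above the fitted one, and calculation B puts it below.

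**The case against.** The strongest case on the other side has four parts.

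- **Scope.** The Section 4.1.6 list follows directly on the rule for subjects unwilling to continue, so it may only say which departing subjects skip the SFV. Section 4.7.2 asks only for notification, Section 4.3.1.1 lets exacerbating subjects stay on product, and Section 4.5.2 keeps subjects after other background changes. This stands as a limit: the broad reading cannot be taken as settled. It does not remove the omalizumab withdrawal. Even on the narrow reading, the rule cuts off subjects whom the same section asks sites to retain.
- **Depot steroid.** A reader might infer that one depot injection, itself a counted exacerbation, ends follow-up. That requires joining three sections under the broad reading, for a route the protocol discourages, and a replacement treatment is not obviously the same thing as one injection for an attack. The injection-treated event would still be counted; only later events would be lost. What stands is a conflict of wording between sections.
- **Missing not at random.** A reader might also infer that the lost time is missing not at random and biases the result in a known direction. The documents do not show this. Calculation B gives no appreciable bias in the fitted ratio when stopping depends only on observed events. Calculation A reverts only active-arm leavers, and it ignores placebo leavers and any benefit of the new treatment. Its upper end, 11% of active-arm time, exceeds the 10% planned for all dropouts.
- **ITT.** Section 4.8.1 defines ITT as randomized and dosed subjects analysed as assigned, and makes no promise of data after other therapy. That is right, so there is no contradiction in the label. A sensitivity analysis may also be in the SAP, which is not shown. It could not replace data that were never collected.

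**Conclusion.** The point holds in limited form. Section 4.1.6 (on at least one reading) and Section 4.5.2 (on either) can end outcome collection for a reason related to the outcome, in an ITT analysis without imputation. Whether this matters depends on whether exacerbation rates change after stopping, and the observed data cannot show that.

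If rates do not change and stopping depends only on observed events, the effect on the primary rate ratio is negligible, and only the presented rates are somewhat low. If rates change, the full-follow-up ITT effect is not estimated. Under the assumed inputs, the full-follow-up ratio lies at about 0.57 to 0.65 against a fitted 0.60. Size and direction are both unknown. The sample size is unaffected. This is an inexpensive improvement to make, not a defect that invalidates the primary test.

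**What to change.** Separate data collection from treatment status in Sections 4.1.6 and 4.5.2. Unless consent is withdrawn or the subject is lost, collect exacerbations, hospitalizations and steroid courses through Week 52 by visit, telephone or records. Do so after product is stopped and after a prohibited medicine or omalizumab is started. Include these data in the ITT analysis, and pre-specify a sensitivity analysis for follow-up ended by such medication.

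Separately, reconcile Sections 4.1.6, 4.3.1.1 and 4.7.2 on depot corticosteroid. It is a counted but discouraged route in Section 4.3.1.1, not permitted in Section 4.7.2, and possibly a reason to end follow-up in Section 4.1.6. Which clinical rule applies is for the sponsor to decide; the data-collection change alters no rule on care.

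The cost is protocol wording and a few extra contacts or record checks. Some subjects will decline, so the gap will narrow but not close.

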4.1.7 Replacement of Subjects

Subjects in this study will not be replaced.

4.1.8 Withdrawal of Informed Consent for Data or Samples

Biological Samples Obtained for the Main Study

Study data are protected by the use of a SID number, which is a number specific to the subject. The investigator is in control of the information that is needed to connect a study sample to a subject. A subject may withdraw consent at any time by notifying the investigator. If consent is withdrawn, any data or samples collected prior to that time may still be given to and used by the sponsor, but no new data or samples will be collected unless specifically required to monitor safety of the subject.

Samples Obtained for Genetic Research (DNA)

Samples obtained for genetic research are protected by the use of a SID number, which is a number specific to the subject. If the subject consents to have his/her samples used for genetic research, this additional research may not start immediately and may start at any time during the storage period. The subject's sample(s), including any specimens of extracted DNA will be stored by the sponsor with similar sample(s) from other subjects at a secure central laboratory. The subject's sample(s) will not be kept for more than 25 years after the end of the study in which they were collected. If the subject chooses not to allow his/her study sample(s) to be used for genetic research, the sample(s) will be destroyed by the sponsor.

If consent is withdrawn after sample(s) have been taken, but before the subject's samples are sent to the sponsor for genetic research, the investigator will arrange to have the sample(s) destroyed. If consent is withdrawn after the subject's sample(s) have been sent to the sponsor for genetic research, the sponsor and the investigator will ensure that these sample(s) are destroyed. However, if the subject's sample(s) have already been used for research, the sponsor is not required to destroy results of this research. In this case only the remaining sample(s) will be destroyed.

4.2 Schedule of Study Procedures

4.2.1 Enrollment/Screening Period

Table 4.2.1-1 shows all procedures to be conducted at the screening/run-in visits. Assessments should be performed in the order shown in the table. The ECG assessments will be performed prior to any blood draws, FE_{NO} , spirometry, and administration of investigational product. In addition, FE_{NO} will be performed prior to spirometry.

Written informed consent and any locally required privacy act document authorization must be obtained prior to performing any protocol-specific procedures, including screening evaluations.

Rescreening

If a subject is to be rescreened, they will be considered a screen failure and will be rescreened with a new SID. All Visit 1 (Week -5) assessments are to be performed, and written informed consent should be obtained again. **Rescreening is generally only permitted once**, when there is a reasonable expectation that the subject will become eligible for the study. Permission to rescreen > 1 time may be granted in the presence of extenuating circumstances and only with prior approval of the medical monitor. Rescreening is not permitted if the reason for screen failure is Inclusion Criterion No. 9 (ACQ eligibility criterion; Section 4.1.2).

Table 4.2.1-1 Schedule of Screening Procedures

Study Period Visit Number Study Week Procedure/Visit Window	Screening Run-in Period						
	1 -5 + 2 D	2 -4 ± 2 D	$\begin{array}{c c} 3 \\ -1 \\ \pm 2 D^{a} \end{array}$				
				Written informed consent/consent for DNA/assignment of SID number	X		
				ePRO device training b	X	X	
Complete ACQ-6 at site in ePRO device	X	X	X				
Home peak flow monitor training and distribution		X					
Distribute ePRO device		X					
Check compliance with PRO assessments			X				
Check compliance and technique with home peak flow meter			X				
Medical and asthma history	X						
Concomitant medications	X	X	X				
Assessment of AEs/SAEs	X	X	X				
Assessment of asthma exacerbations	X	X	X				
Physical examination, height and weight	X						
Vital signs	X	X	X				
ECG ^c	X						
Chest x-ray (if required) ^d	X						
Serum chemistry	X		X				

Template 16.0

Table 4.2.1-1 Schedule of Screening Procedures

Study Period	Screen	ning Run-in	Period
Visit Number	1	2	3
Study Week	-5	-4	-1
Procedure/Visit Window	+ 2 D	± 2 D	± 2 D a
Hematology	X		X
CBC with differentials at local laboratory ^e	X		X
Total serum IgE			X
Urinalysis	X		X
Pregnancy test, serum (females only f)	X		
Hepatitis B, C; HIV-1, HIV-2	X		
QFT-G test	X		
FE _{NO}	X	X	X
Spirometry (pre-BD)	X	X	X
Spirometry (post-BD)	X	X	X
Verify eligibility criteria	X	X	X

ACQ -6 = Asthma Control Questionnaire, omitting FEV1; ACQ -6 = Asthma Control Questionnaire, omitting FEV1; AQLQ(S)+12 = Asthma Quality of Life Questionnaire (Standardised); AE = adverse event; CBC = complete blood count; D = Day; DNA = deoxyribonucleic acid; ECG = electrocardiogram; EQ-5D-5L = European Quality of Life - 5 Dimensions 5 Level Version; ePRO = electronic patient-reported outcome; FENO = fraction of exhaled nitric oxide; FEV1 = forced expiratory volume in one second; HIV = human immunodeficiency virus; IgE = immunoglobulin E; post-BD = post-bronchodilator; pre-BD = pre-bronchodilator; PRO = patient reported outcome; QFT-G = QuantiFERON $^{\text{(R)}}$ -tuberculosis Gold; SAE = serious adverse event; SID = subject identification; TB = tuberculosis; WPAI+CIQ = Work Productivity and Activity Impairment Questionnaire plus Classroom Impairment Questions

- ^a There must be a minimum of 5 days between Visit 3 and Visit 4
- The PRO assessments include Asthma Daily Diary, ACQ-6, AQLQ(S)+12, EQ-5D-5L, WPAI+CIQ. The assessment schedules are programmed into the ePRO device. Subjects will be triggered to complete the appropriate questionnaires/assessments at the appropriate intervals (eg, daily, weekly, biweekly)
- The ECG is to be completed in triplicate until site is notified by sponsor that ECG sub-study is complete
- The chest x-ray may be done at another visit during the screening/run-in period if necessary, as long as results have been reviewed prior to randomization
- The CBC samples should be analyzed as quickly as possible, preferably within 12 hours of sample collection
- The serum pregnancy test will be required of all females in the study regardless of childbearing potential

